MSI-R (AFC, PSC)	Marital Satisfaction Inventory-Revised (Affective Communication, Problem-Solving Communication Subscales)
EDQOL	Eating Disorders Quality of Life
CSQ	Client Satisfaction Questionnaire

PROTOCOL SYNOPSIS

Study Title	Targeting Relationship Domains in Community-Based Treatment of Binge-Eating Disorder
Funder	NIMH
Study Rationale	Clinicians' options for BED treatment are inadequate. Treatments for BED have demonstrated efficacy in controlled settings with specialist therapists and expert supervision, but much less is known about the effectiveness of BED interventions and whether the transition of evidence-based treatments to the community results in poorer outcomes. UNITE activates a key resource by incorporating an important part of the patient's social environment (the partner) into treatment. The investigators hypothesize that UNITE will show preliminary evidence of being superior to CBT-E in achieving binge abstinence via engaging ED-related relationship targets, including improved (a) communication around the disorder, (b) disorder-specific interpersonal problem-solving/ behavioral change skills, and (c) partner-assisted emotion regulation. The investigators will assess targeted relationship domains with observational and speech prosody measures during clinic interactions and self-reports reflecting experiences outside of the clinic. Because the couple is learning how to work together to address BED, the investigators hypothesize that maintenance of gains will show evidence consistent with superiority in UNITE.
Study Objective(s)	Primary 
• To compare the effectiveness of UNITE versus CBT-E in achieving abstinence from binge-eating. Secondary 
• To compare the effectiveness of UNITE versus individual CBT-E in decreasing ED-related psychopathology, depression, and anxiety.• To compare target relationship domains in patients and partners.• To compare treatment satisfaction and ED-related quality of life in UNITE versus CBT-E

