---------------------------	---

Outcomes	
Primary outcome: Eating Disorder Examination-Questionnaire (EDE-Q) abstinence from binge eating (Fairburn & Beglin, 1994).
 
Secondary outcomes will include ED symptoms, depression and anxiety, couple-based measures, treatment satisfaction, and quality of life. ED symptoms will be measured with the Eating Disorder Examination-Questionnaire (EDE-Q; 28 items) binge frequency and global score (Fairburn & Beglin, 1994), the Binge Eating Scale (BES; 16 items) which measures binge eating severity (Gormally et al., 1982), and the Yale-Brown Obsessive Compulsive Scale Modified for Binge Eating (Y-BOCS-BE; 10 items) which measures the obsessiveness of binge-eating thoughts and compulsiveness of binge-eating behaviors (Deal et al., 2015). Beck Depression Inventory-II (BDI-II; 21 items) and Beck Anxiety Inventory (BAI; 21 items) will measure severity of current depressive and anxiety symptoms, respectively (Beck et al., 1988; Beck et al., 1996). Difficulties in Emotion Regulation Scale (DERS; 36-item) and the partner version (DERS-Partner; 8 items) will measure emotion regulation in oneself and one's partner, respectively (Gratz & Roemer, 2004). Dyadic Adjustment Scale (DAS; 32 items) and DAS-4 (4 items) will measure relationship satisfaction. Communication Patterns Questionnaire-Short Form (CPQ-SF; 12 items (Christensen & Heavey, 1990) modified for BED has two scores that will be calculated to assess how the couple communicates about the ED. These are a total score made up of the Self Demand/Partner Withdraw and Partner Demand/Self Withdraw subscales (6 items) and the Constructive Communication subscale (3 items). Marital Satisfaction Inventory (MSI-R; 32 items) affective communication (AFC) and problem-solving/communication (PSC) subscales will be used (Snyder, 1997). Treatment satisfaction will be measured with the Client Satisfaction Questionnaire (CSQ; 18 items). (Nguyen et al., 1983). Eating

-----------------	---

Disorders Quality of Life (EDQOL; 26 items) will measure the extent to which the ED affects quality of life (Engel, 2003). ED-related measures will be given to patients only and all other measures will be given to patients and partners.	

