Statistical and Analytic Plan	Intent-to-treat or modified intent-to-treat, if appropriate, will comprise the primary approach. Differential treatment effects will be analyzed with multilevel mixed-effects models with fixed effects and interactions for Time, Treatment, and (where appropriate) Participant Status (i.e., patients/partners), and with random effects to address clustering.
Data and Safety Monitoring Plan	The DSMG will be responsible for data quality management and ongoing assessment of participant safety.

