3.2 Study Duration, Enrollment and Number of Subjects

38 couples will be enrolled over 18 months (to aim for 34 couples who complete the intervention). Each couple will be randomized to either UNITE or CBT-E and will undergo 16 weeks of treatment, followed by follow-up assessments at the end of treatment and 3- and 6-months after the end of treatment.

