5 STUDY EVALUATIONS AND MEASUREMENTS

5.1 Efficacy Evaluation

Preliminary efficacy (e.g. changes in binge-eating frequency, depression, anxiety, and relationship functioning) of UNITE will be assessed in comparison to the control group (CBT-E). Treatment gains will be assessed including observational and self-report measures. The primary outcome is abstinence from binge eating over the past 28 days measured with the EDE-Q. Secondary outcomes include EDE-Q binge frequency and global psychopathology, BES, Y-BOCS-BE, BDI-II, BAI, DERS, DERS-Partner, DAS, DAS-4, CPQ-SF, MSI-R (AFC and PSC), CSQ, and EDQOL.

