5.3 Statistical Methods

- **Baseline Data.** Sociodemographics and baseline clinical characteristics will be summarized with descriptive statistics.
- **Efficacy Analysis.** Study hypotheses will be tested using intent-to-treat or modified intent-to-treat methods, as appropriate. For patient-only outcomes, differential treatment effects will be tested with multilevel mixed-effects models with fixed effects and two-way interactions for Time and Treatment and a random effect for Patient. For outcomes assessed in both patients and partners, differential treatment effects will be tested with multilevel mixed-effects models with fixed effects and two- and

three-way interactions for Time, Treatment, and Participant Status (i.e., Patient or Partners) and random effects for Participant and Couple. Linear, logistic, and Poisson distribution functions will be used to model outcome variables. Treatment satisfaction, assessed at post-treatment only, will be compared between patients in UNITE and CBT-E with linear regression.

- **Safety Analysis.** Adverse events will be summarized as a numerator (total affected) and denominator (number at risk) for patients and partners in each treatment arm using the ClinicalTrials.gov categories of all-cause mortality, serious adverse events, and other (not including serious) adverse events.

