7 STUDY INTERVENTION ADMINISTRATION

- **Randomization:** The study statistician will write a computer program to perform a stratified random assignment to the initial two conditions on a 1:1 basis using a permuted block algorithm.

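### The patient-partner model has no visit-specific covariance within couples, so two of its change contrasts get wrong standard errors if same-visit residuals correlate

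*Combined protocol and SAP*

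**What the plan says.** Section 5.3 (Efficacy Analysis) has two model sentences. Patient-only outcomes get one random effect, for Patient. Outcomes assessed in both members get "three-way interactions for Time, Treatment, and Participant Status (i.e., Patient or Partners) and random effects for Participant and Couple". The synopsis row on the statistical plan adds only that models are fitted "with random effects to address clustering". Neither place says whether the effects are intercepts or slopes. Neither names a couple-by-visit term, a residual covariance between members, a robust variance, the coding of Participant Status, or a significance level.

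The synopsis (Outcomes) sets the scope: "ED-related measures will be given to patients only and all other measures will be given to patients and partners". The two-member model therefore covers DAS, CPQ-SF, MSI-R, DERS, DERS-Partner, BDI-II and BAI. It serves a listed secondary objective: "To compare target relationship domains in patients and partners". It does not cover the primary endpoint. Section 5.1 states: "The primary outcome is abstinence from binge eating over the past 28 days measured with the EDE-Q", which is a patient measure.

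Section 5.4 gives no power calculation. It defends 38 couples on the ground that a cited simulation study found 20 groups enough for standard errors without bias.

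**The concern.** An intercept is the same at every visit, so it drops out of any change over time. Once Participant and Couple intercepts have dropped out, the model has nothing left to link a patient's change to the partner's change. It counts each couple as supplying two independent changes.

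That is doubtful for DAS, CPQ-SF and MSI-R, where both people rate one relationship at the same visit. A good or bad month for the couple would move both scores. If so, averaging over members overstates the information on the treatment difference in change, and comparing members understates it. The relationship targets are the trial's hypothesised mechanism, and these models supply the evidence on them. Section 5.4 also rests the sample size on having trustworthy standard errors.

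**Working it through.** The plan gives no standard error, power or error rate for these outcomes, so there is no figure of its own to reproduce.

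**Inputs from the documents.** 38 couples enrolled, 34 expected to complete (section 3.2). 1:1 allocation (section 7), taken as 19 couples per arm, or 17 for completers. Five visits: pre, mid, post, 3 months, 6 months (sections 4.1 to 4.3, Table 3).

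**Assumptions.** Intercepts only; categorical Time; linear model; balanced data; equal residual variance in patients and partners; two-sided 5% level. The same-visit residual correlation between members, rho, is not given and is varied from -0.2 to 0.5.

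**Step 1: the model.** Score = fixed effects + Couple intercept + Participant intercept + residual with variance s². The Couple intercept gives the two members the same covariance at every pair of visits, including the same visit. Both intercepts cancel from a change between two visits.

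**Step 2: variances of the treatment difference in change, n couples per arm.**

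| Contrast | True variance | Variance the model uses |
|---|---|---|
| Member-averaged | 2s²(1+rho)/n | 2s²/n |
| Patient minus partner (three-way) | 8s²(1-rho)/n | 8s²/n |
| One member only | 4s²/n | 4s²/n |

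The fitted residual variance averages the couple-mean and within-couple parts, [(1+rho)+(1-rho)]s²/2 = s². It is right on average but wrong for each of the first two contrasts. The true SE is sqrt(1+rho) times the reported one for the member-averaged contrast and sqrt(1-rho) times for the three-way contrast.

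**Step 3: actual size of a nominal 5% test on 1 df.** Size = 2[1 - Phi(1.96/ratio)], where ratio = true SE / model SE. At rho = 0.3: 1.96/1.140 = 1.719 gives 8.6%, and 1.96/0.837 = 2.342 gives 1.9%.

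| rho | Ratio, member-averaged | Size | Ratio, three-way | Size |
|---|---|---|---|---|
| -0.2 | 0.894 | 2.8% | 1.095 | 7.4% |
| 0 | 1.000 | 5.0% | 1.000 | 5.0% |
| 0.1 | 1.049 | 6.2% | 0.949 | 3.9% |
| 0.3 | 1.140 | 8.6% | 0.837 | 1.9% |
| 0.5 | 1.225 | 11.0% | 0.707 | 0.6% |

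**Step 4: simulation under no treatment effect** (40,000 trials per setting, five visits, 19 per arm). The 1-df sizes agree: 8.5% / 2.0% at rho 0.3 and 10.8% / 0.6% at 0.5. A joint 4-df test over all visits is further off: 7.2% / 3.2% at 0.1, 11.9% / 0.9% at 0.3, 17.6% / 0.1% at 0.5. The patient-only contrast stays at 4.8% to 5.1% throughout. With 17 per arm the results are the same within simulation error.

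**Step 5: REML fits of the stated model** (606 simulated trials, rho 0.3, 19 per arm, s² = 1, Treatment and Status coded +1/-1). In this coding the true SEs are sqrt(1.3/38) = 0.185 and sqrt(0.7/38) = 0.136, and the model's value is sqrt(1/38) = 0.162. The fits reported 0.162 for both terms, and 1-df sizes were 8.7% / 2.8%. The Couple intercept did not rescue the contrasts: its variance rose only from 1.00 to about 1.09, and the residual stayed at 1.00.

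**Step 6: the same data with a Couple-by-visit effect added.** The reported SEs became 0.185 and 0.135. The 1-df sizes became 4.8% / 6.1%; the Monte Carlo standard error is sqrt(0.05 x 0.95/606), about 0.9 percentage points. In the balanced calculation with separate couple-level and within-couple error terms, 4-df sizes were 4.9% to 5.1% (member-averaged) and 4.9% to 5.4% (three-way) for rho from -0.2 to 0.5.

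**The case against.** Several points on the other side stand and limit the claim.

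- A reader might infer that the model allows no covariance at all between members at the same visit. It does: a Couple intercept supplies a constant one. Only the additional visit-specific part is missing.
- Section 5.3 does not say intercepts only, and a couple-level time slope would carry some of the shared change. Intercepts are still the plain reading, and the single Patient effect in the companion sentence fits it.
- A reader might take the liberal direction for the member-averaged test as established. It is not. The relevant rho is what remains after stable participant and couple differences are removed, so strong raw agreement between members does not fix its size or sign. The shared-relationship argument suits DAS, CPQ-SF and MSI-R. It is weaker for BDI-II, BAI and DERS, where each person reports their own state. Joint sessions occur only in UNITE.
- The plan does not say that a member-averaged contrast will be reported. If Participant Status is reference-coded, the two-way term is one member's effect and its size is essentially nominal. The three-way result does not depend on that coding.
- The trial is described as preliminary, and section 5.4 disclaims power for all hypotheses. No power is planned for the three-way test, so no loss of planned power can be claimed.

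What does not stand is the view that this is only missing detail. The stated model, read plainly, gives wrong standard errors for two contrasts at any non-zero rho. Having more than 20 couples does not cure that, so the argument in section 5.4 does not answer it.

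**Conclusion.** The concern holds conditionally. With intercepts only, any same-visit residual correlation between patient and partner biases the standard errors of the member-averaged Time x Treatment contrast and the three-way contrast, in opposite directions. Over rho 0.1 to 0.5 the true SE is about 1.05 to 1.22 times the reported one for the first and 0.95 to 0.71 times for the second; the corresponding test sizes are in the Step 3 table. A negative rho reverses both directions.

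The figures rest on the assumptions listed with the inputs. Dropout, the logistic and Poisson models, and the weekly DAS-4 (which partners in CBT-E do not complete, section 4.2) were not checked.

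A reader might infer that the trial's main comparison is compromised. The documents do not support that: binge abstinence is analysed in patients alone. The point concerns secondary outcomes measured in both members, and it is worth correcting because the remedy is small and works for either sign of rho.

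**What to change.** In section 5.3, for every outcome measured in both members, add a residual covariance that lets patient and partner residuals at the same visit correlate, with either sign allowed. A Couple-by-visit random effect is an alternative if only positive correlation is expected, since a variance component cannot represent a negative one. Keep the Participant and Couple effects and all fixed effects as they are.

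The cost is one sentence and one more covariance parameter. Member-averaged intervals widen by about 5% to 22% for rho 0.1 to 0.5, which is the correction of an understated error. Over the same range, three-way intervals narrow by about 5% to 29% (1 - 0.949 to 1 - 0.707).

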5.4 Sample Size and Power

While there is not universal agreement about the minimum number of higher-level groups required to produce stable estimates in multilevel models, Maas and Hox's (2005) definitive simulation study of bias in higher level effects demonstrates that a sample size of 20 groups (which are couples in this case) is sufficient to produce unbiased estimates of standard errors. Thus, while the sample size of 38 couples does not result in power to test all study hypotheses, the sample size of 38 couples is adequate to perform unbiased analyses using multilevel mixed-effects models.

5.5 Interim Analysis

Problems with participant recruitment, dropouts, or data management would be most likely to trigger the need for stopping the protocol. However, adverse events also would be a possible reason as would a clear finding of superiority for one treatment arm prior to the completion of the protocol. It is unlikely that any new information will become available that would necessitate stopping the trial. It is possible that excessive study dropouts and missing data would limit the data analysis. The investigators have powered the study expecting dropouts. The investigators acknowledge that there may be situations that occur that might warrant stopping the trial that are not covered here.

6 STUDY INTERVENTION (intervention details)

- **Description:** see Background and Rationale "Name and Description of Intervention"
- **Treatment Compliance and Adherence**
Given the substantial interruption to the trial due to the Covid-19 pandemic (i.e., initial couples receiving face-to-face care; some couples having a portion of treatment face to face and transitioning to virtual, other couples having fully virtual treatment) our adherence measures were limited to assurances by the supervisors (who reviewed audio-recordings of all sessions) that therapists were adhering to the treatments as laid forth in the manuals. As funding for personnel continued even when the trial was interrupted, adequate funds for extensive compliance/adherence assessments were not available.

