The investigators have incorporated partners in the treatment of adult psychiatric disorders, using adaptations of cognitive-behavioral couple therapy (CBCT) (Abramowitz et al., 2013; Baucom et al., 2017; Baucom et al., 1998; Sher et al., 1990). The investigators demonstrated initial efficacy of our couple-based ED treatments in a university hospital specialist setting (Baucom et al., 2017; Bulik et al., 2011; Kirby et al., 2015). The investigators developed a CBCT intervention for BED/BN (UNiting couples In the Treatment of Eating disorders [UNITE]). Here the investigators test the preliminary comparative effectiveness of UNITE versus individual CBT-enhanced (CBT-E) (a transdiagnostic treatment for EDs) in a small randomized controlled trial (RCT) of 28 couples in a community clinic. Because UNITE activates a key resource by incorporating an important part of the patient's social environment (the partner) into treatment, the investigators hypothesize that UNITE will show preliminary evidence of being superior to CBT-E in achieving binge/purge abstinence via engaging ED-related relationship targets, including improved (a) communication around the disorder, (b) disorder-specific interpersonal problem-solving/ behavioral change skills, and (c) partner-assisted emotion regulation. Targeted relationship domains will be assessed with observational and speech prosody measures during clinic interactions and self-reports reflecting experiences outside of the clinic. Because the

couple is learning how to work together to address BED/BN the maintenance of gains are hypothesized to show evidence consistent with superiority in UNITE.

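### Section 5.5 says the study was powered with dropout in mind, but no power calculation is documented, and under illustrative assumptions power for a moderate difference in abstinence is low

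*Combined protocol and SAP*

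**What the plan says.** Section 5.5 (Interim Analysis) discusses what might stop the trial. It notes that heavy dropout and missing data could limit the analysis, and then answers that risk with: "The investigators have powered the study expecting dropouts".

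Section 5.4 (Sample Size and Power) is the only place where the sample size is justified. It cites a simulation study for the statement that "a sample size of 20 groups (which are couples in this case) is sufficient to produce unbiased estimates of standard errors", then says that "the sample size of 38 couples does not result in power to test all study hypotheses" but that this number is adequate for unbiased multilevel analyses.

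On numbers, section 3.2 says "38 couples will be enrolled over 18 months (to aim for 34 couples who complete the intervention", and the synopsis agrees. Section 7 allocates couples 1:1. Section 5.1 defines the endpoint: "The primary outcome is abstinence from binge eating over the past 28 days measured with the EDE-Q". Section 1.3, by contrast, describes the present trial as a "small randomized controlled trial (RCT) of 28 couples in a community clinic".

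**The concern.** A reader of 5.5 is told that power was secured and that dropout was built into it. A reader who then turns to 5.4 finds no power figure and none of the inputs to one. The justification offered there concerns bias in standard errors. An estimate can have an unbiased standard error and still be far too imprecise to detect a plausible effect, so the 20-group rule cannot stand in for a power argument.

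Abstinence is the single primary outcome, and comparing it between arms is the primary objective in the synopsis. If the trial is described as powered, a non-significant abstinence result may be taken as evidence that UNITE and CBT-E do equally well, when the confidence interval would still include large differences in either direction.

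**Working it through.** **Inputs from the plan.** 38 couples enrolled and 34 expected to complete (synopsis, 3.2); 1:1 allocation (section 7); binary primary outcome, with one patient per couple (5.1, synopsis). This gives 38/2 = 19 patients per arm enrolled and 34/2 = 17 per arm completing.

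**Inputs the plan does not give.** Alpha, sidedness, target power, abstinence rates and the size of difference sought. No stated power can therefore be reproduced. The figures below are illustrative and assume a two-sided 5% level, an unadjusted comparison at one time point, and CBT-E abstinence of 30% to 50%.

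**Step 1: the dropout allowance.** Implied loss = (38 − 34)/38 = 4/38 = 10.5%. In reverse, 34/(1 − 0.105) = 38.0. A round 10% gives 34/0.90 = 37.8, which also rounds up to 38. The allowance is arithmetically coherent.

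**Step 2: power for a 20-point difference.** For each possible pair of abstinence counts in the two arms, the two binomial probabilities were multiplied, and the products were summed over the pairs that reach p ≤ 0.05. For 30% v 50%:

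| Patients per arm | Fisher exact | Pooled chi-square |
|---|---|---|
| 19 (38 couples) | 17.2% | 26.0% |
| 17 (34 couples) | 13.6% | 23.0% |

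The usual normal-approximation formula gives 23.7% and 21.6%. Other control rates change little: 40% v 60% with 19 per arm gives 16.6% (Fisher).

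**Step 3: difference detectable with 80% power, 19 per arm.** The UNITE rate was raised until the same enumeration reached 80%:

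| CBT-E abstinence | Chi-square | Fisher |
|---|---|---|
| 30% | 43.9 points | 47.5 points |
| 40% | 41.8 points | 45.8 points |
| 50% | 39.5 points | 42.8 points |

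The range is about 40 to 48 points.

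**Step 4: precision.** With abstinence p in both arms and n per arm, the 95% half-width for the difference is 1.96 × √(2p(1 − p)/n).

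- p = 0.5, n = 19: 1.96 × √(0.50/19) = 0.318, or ±32 points.
- p = 0.5, n = 17: 1.96 × √(0.50/17) = 0.336, or ±34 points.
- p = 0.2, n = 19: 1.96 × √(0.32/19) = 0.254, or ±25 points.
- p = 0.2, n = 17: 1.96 × √(0.32/17) = 0.269, or ±27 points.

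**Step 5: the 28 couples in 1.3.** This is 1 − 28/38 = 26% below the enrolment figure and 1 − 28/34 = 18% below the completer figure, so it matches neither.

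**The case against.** Five points can be made for the plan.

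- *Section 5.4 disclaims power only for all hypotheses.* This stands. Not all is weaker than none, and the text leaves open that some hypothesis, possibly the primary one, was considered powered. A reader might infer that 5.4 concedes the trial is unpowered, or that the claimed power is shown not to exist. The documents do not support either statement. They show that no power is documented and that 5.5 is in tension with 5.4.
- *Dropout was allowed for.* This stands too. The 38-to-34 allowance is real and consistent, and only the word powered lacks support.
- *The trial is presented throughout as small and preliminary, and the sentence sits in a paragraph about stopping.* This lowers the chance of a misreading. It does not make the sentence accurate, and the sentence is the plan's own answer to the risk of dropout.
- *The planned analysis is a repeated-measures logistic mixed model, not a two-proportion test.* The true power may differ somewhat, so the figures are illustrative. Section 5.4 offers no calculation under the planned model to put in their place.
- *The 28-couple figure is background text.* Agreed: it is a separate inconsistency. A reader might infer that it bears on power, but it does not.

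It is also tempting to say that the 20-group rule counts the wrong units, because the primary outcome is measured in patients only. With one patient per couple, 38 couples are 38 patients, so that argument has no force.

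**Conclusion.** The claim of power in 5.5 is undocumented. The only justification given for 38 couples addresses bias in standard errors, and the same section limits what the sample can test. For the primary comparison the claim does not hold for moderate differences: power for 30% v 50% abstinence is about 17% to 26% with 19 per arm and 14% to 23% with 17, and 80% power with 19 per arm is reached only at about 40 to 48 points. These figures assume a two-sided 5% level, 1:1 allocation, an unadjusted comparison at one time point and, for the detectable difference, control rates of 30% to 50%. The absence of a power calculation depends on none of these assumptions. This should be corrected. It does not invalidate the design, which the plan describes as preliminary.

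**What to change.** 1. **Section 5.5.** Replace the sentence with: *Enrolment of 38 couples allows for about 10% loss (34 completers); the study is not formally powered for the abstinence comparison.* If a calculation does exist, insert it instead in 5.4, with its alpha, sidedness, abstinence rates, dropout rate and resulting power or detectable difference.
2. **Section 5.4.** Add the expected precision with its conditions: for an unadjusted difference at one time point, a 95% half-width of about ±32 points with 38 couples and ±34 with 34 if abstinence is near 50%, or about ±25 and ±27 if it is near 20%. State that the abstinence difference will be reported with its confidence interval and that non-significance will not be read as equivalence.
3. **Section 1.3, separately.** Reconcile the 28 couples with the 38 in the synopsis, 3.2 and 5.4.

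The cost is wording only: no change to enrolment, assessments or analysis model. The plan's description of itself becomes less favourable.
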